### **7.3.9 Early Termination Assessments**

Early Termination (ET) assessment for post-baseline efficacy, laboratory or vital sign data will be mapped to the End of Study (Week 24) visit.

### **7.3.10 Randomization Strata**

As described in [Section 6](#), randomization is stratified by study site. Furthermore, protocol indicates that analysis will include adjustment for study site. There are approximately 45 study sites and it is likely that some of these study sites will have small number of subjects that are

included in the mITT population and thus could lead to unreliable treatment effects estimates and p-values. With this, the study sites will be pooled by state and then by region. However, if a state has significantly large number of subjects (eg almost double) compared to the other regions, it will be considered as one of the final pooled sites. The resulting final pooled sites (referred to as 'site' from here on) are as follows:

[REDACTED]

#### 7.4 Conventions

All data listings, summaries, figures and statistical analyses will be generated using SAS version 9.4 or higher.

Subjects will be randomized to 1 of 2 treatment groups (SP-102 or placebo) and will receive 1 injection at Baseline (D1). After 4 weeks, an additional injection of SP-102 may be administered to all subjects regardless of the treatment they were originally randomized to. Because of this, baseline, efficacy, and safety variables will be summarized in two ways.

The first will summarize data for the 2 randomized treatment groups for the primary analysis period. Subjects will be analyzed in either the SP-102 or placebo treatment groups. Baseline summaries and data for this first 4 weeks will be summarized using the following treatment columns. Only baseline data will have the overall column.

SP-102	Placebo	Overall
--------	---------	---------

The second will classify subjects into 1 of 4 groups and will summarize data for the secondary analysis period. These 4 groups include the following:

- Subjects who receive only 1 SP-102 injection
- Subjects who receive 2 SP-102 injections

- Subjects who receive only 1 placebo injection
- Subjects who receive 1 placebo injection and 1 SP-102 injection

The 4 treatment groups will be used in the summary and analyses involving the secondary analysis period (randomization through end of study).

These 4 groups may be combined for additional analyses (eg, combine into one group any subject who received an injection of SP-102 at any point in time).

[REDACTED]

SP-102/SP-102	PBO/SP-102	SP-102/none	PBO/none	Overall
---------------	------------	-------------	----------	---------

Overall columns are to be included within the table shells as follows:

Data	Column labels
Demography	Treatment and overall
Baseline	Treatment and overall
Disposition	Treatment and overall
Prior Medications	Treatment and overall
Concomitant Medications	Treatment and overall
Efficacy	Treatment
AEs	Treatment
Other safety	Treatment

Listings will be sorted in the following order: treatment group, subject, parameter, and visit unless otherwise stated. All data will be listed. Subjects who were not randomized will be displayed after the randomized treatment groups.

Continuous variables will be summarized by the number of non-missing observations, mean, median, standard deviation, and minimum and maximum. For all tabulations of changes from

baseline data, the lower and upper 95% confidence limits for the mean for the individual treatments will be given.

Categorical variables will be summarized by presenting the frequency and percent. Percentages will be based on the number of non-missing observations or the subject population unless otherwise specified. For each variable, all categories will be shown. Zero frequencies (but not the percent) within a category will be presented.

#### **7.4.1 Decimal Places**

Decimal places for derived data described in [Section 7.2](#) will be determined by the scale of measurement unless otherwise stated. No decimal places will be displayed if the smallest calculated value is  $\geq 100$ ; 1 decimal place will be displayed when the smallest value is within the interval (10, 100), with 10 being inclusive; 2 decimal places will be displayed when the smallest value is within (1, 10), with 1 being inclusive; and so on for even smaller scales of measurement.

If derived data such as number of days or total score is an integer, then it will be presented with zero decimal places.

Means, medians and percentiles will be displayed to one more decimal place than the data, dispersion statistics (e.g. standard deviation) will have two more decimal places, and the minimum and maximum will be displayed to the same number of decimal places as reported in the raw data. Percentages will be displayed with one decimal place.

P-Values will be quoted to 3 decimal places. P-values  $< 0.001$  will be presented as  $p < 0.001$ . If this value is less than 0.05, 0.01 or 0.001, attention will be drawn to this fact using the conventional “\*”, “\*\*” or “\*\*\*” annotation, respectively.

### **7.5 Subject Disposition**

Subject disposition will be summarized as follows:

- The number of subjects randomized, and number in each analysis population (Safety, mITT, and Per Protocol) will be summarized by treatment group and overall based on all randomized subjects for both the primary and secondary analysis periods.
- The number of subjects screened, who failed screening and the reasons for failure will be summarized using the Screened Population.
- The number of early termination and the reasons for termination will be tabulated by treatment group and overall for each analysis period for the Safety Analysis Population.

- The number of subjects who are Primary Efficacy Endpoint Completers, 12-Week Completers, and 24week Completers will be summarized by treatment group and overall for the Safety Analysis Population.

## 7.6 Protocol Deviations

Protocol deviations will be collected by study site and grouped into different categories, such as those who:

- [Redacted]
- [Redacted]
- [Redacted]
- [Redacted]
- [Redacted]

Major protocol violations that impact the primary efficacy analysis may lead to exclusion from the PP population. Protocol deviation categories will be summarized for the safety analysis population by treatment group and overall. Protocol deviations will be summarized separately for the primary and secondary analysis periods.

A listing of protocol deviations will be provided within Appendix 16.2.

## 7.7 Baseline Comparability

The comparability of treatment groups with respect to subject demographics and baseline characteristics will be assessed in a descriptive manner, but no formal statistical testing will be performed.

Standard continuous or categorical variable summaries will be presented by treatment group based on the Safety Analysis Population.

Baseline demographic data will be summarized using the Safety Analysis Population for both the primary and secondary analysis periods. This will include age in years, gender, fertility status (childbearing potential, post-menopausal, surgically sterile), ethnicity, race, height, weight, and BMI.

## 7.8 Medical History

Summary table of previous and ongoing conditions at screening will be presented by treatment group and overall for the Safety Analysis Population. Conditions will be presented by Medical

Dictionary of Regulated Activities (MedDRA) version 23.1 (or a more up-to-date version by the time of database lock) primary system organ class and preferred term. Listings of all medical history will be presented.

## 7.9 Prior and Concomitant Medications

[figure not shown]
Summary tables will be produced for prior and concomitant medications presented by treatment group and overall for the Safety Analysis Population. Prior medications are defined as all medications that started and stopped before the date of first dose of study drug. Prior medications will be summarized by the planned treatment for the first injection (SP-102, Placebo).

Concomitant medication refers to all drugs and therapies that started prior to, on, or after the first dose of the study medication and ended on or after the date of the first dose of the study medication, or are ongoing at end of study. Medications are coded using WHODDE B3 Global - Sep 2019 Concomitant medications will be summarized using Anatomical Therapeutic Chemical [ATC] Level 2. Listings of all prior and concomitant medications will be presented. Concomitant medications will be summarized for each post randomization treatment period as follows:

- First four weeks: summarizes all drugs and therapies taken within first 4 weeks after first dose of study medication. This will be tabulated using the two treatment groups: SP-102, Placebo.
- Entire treatment period: summarizes all drugs and therapies that started prior to, on, or after the first dose of the study medication and ended on or after the date of the first dose of the study medication. This will be tabulated using the treatment group with four arms: SP-102/SP-102, PBO/SP-102, SP-102/none, PBO/none.
- Through 12 weeks: summarizes all drugs and therapies taken within first 12 weeks after first dose of study medication. This will be tabulated using the treatment group with four arms: SP-102/SP-102, PBO/SP-102, SP-102/none, PBO/none, and by exposure to SP-102, that is, Exposed vs. Not Exposed to SP-102. The Exposed group will include the subjects that have received SP-102 for index injection and/or have repeat injection while Non-Exposed group will include the subjects that have received Placebo for index injection and do not have repeat injection

## 7.10 Exposure to Study Drug

The number of randomized subjects that received index injection, that received repeat injection, and that received any injection will be summarized by treatment group.

## 7.11 Treatment Compliance

Compliance will not be calculated but the listing of study drug administration will be provided.

## 7.12 Efficacy Analyses

All statistical tests will be performed using a two-tailed 5% overall significance level, unless otherwise stated. All comparisons between treatments will be reported with 95% confidence intervals (CI) for the difference. Pain profiles through the first four weeks will be presented by the treatment received for the first injection (SP-102, Placebo). Moreover, pain profiles through 12 weeks will be presented by treatment received for second injection (SP-102/SP-102, PBO/SP-102, SP-102/none, PBO/none). Also, the ‘site’ indicated in this section refers to the final pooled sites as described in [Section 7.2.10](#).

### 7.12.1 Primary Endpoint

The primary efficacy endpoint is the mean change from Baseline (D1) to Week 4 in the mean NPRS average pain score in the affected leg.

The null and alternative hypotheses are:

- [Redacted]
- [Redacted]

The NPRS is an 11-point scale (0 to 10-point scale where 0 is no pain and 10 is most severe pain) that allows the subject to rate the severity of their pain intensity at various points in time. Twice daily: in the morning and evening (approximately 12 hours apart), the subject will use the NPRS to record their average and worst pain in the past 12 hours. [Redacted]

[Redacted] After the Screening Visit, the NPRS will be collected twice daily using the eDiary through Week 12; thereafter, the NPRS will be collected at clinic visits only.

### 7.12.2 Primary Efficacy Analysis

The primary comparison will use a linear contrast of the least squares (LS) means comparing the mean weekly mean scores up to Week 4 (average of Weeks 1, 2, 3, and 4 change from baseline LS means estimated from the model).

For each type of pain score collected, NPRS scores will be summarized on a weekly basis (Weeks 1, 2, 3, and 4). The LS means, its corresponding standard errors and 95% CI will be presented for all four weeks. The same will be presented for the mean LS mean corresponding to the mean weekly mean scores across all four weeks. The estimate of the LS mean treatment difference, its standard error, and 95% CI will be presented for the average LS mean across all four visits.

The SAS code anticipated to be used for the analysis of the primary efficacy endpoint is as follows:

### 7.12.3 Sensitivity Analysis

The following sensitivity analysis will be applied;

1. The primary analysis will be re-run for the PP Population.
2. The primary analysis model will be re-run but will include sex, duration of leg pain, prior opioid use for current episode of pain (yes/no) as additional factors in the model. Prior opioid use for current episode of pain will be determined by reviewing all the subject's medications and checking if there is any medication with opioid (using the ATC3 codes as listed below) and comparing the medication's start date and end date to the current episode date, that is, for the subject to be classified as having a prior opioid use for current episode of pain ('yes'), the current episode date should be within the medication's start date and end date:

- N02A (Opioids)
- A07D (Antipropulsives)
- R05D (Cough suppressants, excl. combinations with expectorants)
- R05F (Cough suppressants and expectorants, combinations)

Duration of leg pain is the number of months from start date of current episode of lumbosacral radicular pain to D1. That is,

[ D1 visit date – start date of current episode of lumbosacral radicular pain + 1 ] / 30.

The following SAS codes will be used to implement the placebo-based pattern mixture imputation.

[REDACTED]

The imputed data sets will be analyzed with the same MMRM model employed in the primary analysis and then summarized using PROC MIANALYZE.

#### **7.12.4 Key Secondary Endpoints**

The key secondary efficacy endpoint is the change in ODI total score from Baseline (D1) to Week 4.

The ODI is a widely accepted and validated measure for measuring degree of disability and estimating quality of life in a person with low back pain. The ODI is a questionnaire completed by the subject which contains 10 topics concerning intensity of pain, lifting, ability to care for oneself, ability to walk, ability to sit, sexual function, ability to stand, social life, sleep quality, and ability to travel. Each topic category is followed by six statements describing different potential scenarios in the subject's life relating to the topic. The subject then checks the statement which most closely resembles their situation. Each question is scored on a scale of 0-5 with the first statement being zero and indicating the least amount of disability and the last statement is scored 5 indicating most severe disability. The scores for all questions answered are summed, then multiplied by 2 to obtain the index (0 to 100). If a subject misses some questions, the total score of the answered questions will be divided by the total expected score (number of answered questions times 5) then multiplied by 100 (Fairbank). The ODI index obtained using this algorithm is equivalent to the ODI index obtained by summing all the scores then multiplying it by 2 in the event that there are no skipped or missed questions. A subject would need to answer at least seven questions out of ten before a total score is calculated for that visit. Zero is equated with no disability and 100 is the maximum disability possible. The ODI will be obtained at the Screening, Baseline (D1), Week 4 (Day 29), Week 12 (Day 85), and Week 24 (Day 169) visits.

#### **7.12.5 Key Secondary Analysis**

Baseline ODI is defined as the last ODI assessment score prior to the first injection on D1. The change in ODI total score from baseline will be analyzed using the mITT and PP Analysis Populations. This endpoint will be analyzed using the analysis of covariance (ANCOVA) model where change from baseline in ODI score at Week 4 will be the response variable with fixed effects for treatment (two groups: SP-102 or placebo), site, Pain Catastrophizing Scale group (<30 or

≥30), and baseline ODI. The treatment group categories for this analysis will be the SP-102 and placebo groups. A summary of the observed and change from baseline ODI total score will be presented by visit and treatment group jointly for both the primary and secondary analysis periods. Listings of all 10 topic scores and total scores will be presented.

The following SAS code will be used for this key secondary analysis;

[REDACTED]

## 7.12.6 Other Secondary Endpoints and Analysis

All other secondary endpoints (outlined below) will be analyzed using the mITT and PP Analysis Population.

### 7.12.6.1 PGIC at Week 2, Week 4, Week 8, and Week 12.

The PGIC is a seven-point scale (1 to 7, where 1 is very much improved and 7 is very much worse) that allows patients to rate their global impression of change. PGIC will be collected after randomization at Weeks 2, 4, 8, 12, 16, 20, and 24. For analysis, a subject will be classified as either PGIC responder, that is, a PGIC response of 1: very much improved or 2: much improved or a PGIC non-responder, that is, all other PGIC responses (recorded as 3-7 in the scale). Subjects who do not complete the measure at the timepoint of interest will also be considered non-responders. The number and percentage of subjects reporting each of the seven PGIC response levels will also be summarized by visit and treatment. The analysis will utilize separate Chi-Square tests for Week 2 and Week 4 where the p-value of the treatment difference will be presented. Separate logistic regression models with treatment, site, and Pain Catastrophizing Scale group as factors will also be used to compare the treatment groups at each week (Week 2 and Week 4) using the two treatment groups. The odds ratio of SP-102 vs placebo at Weeks 2 and 4, and its corresponding 95% CI and p-value will be presented.

Separate Chi-Square tests and similar logistic regression analyses will be applied at Weeks 2, 4, 8, and 12 using the treatment group with four arms: SP-102/SP-102, PBO/SP-102, SP-102/none, PBO/none. The following odds ratios at Weeks 2, 4, 8, and 12 and the corresponding 95% CIs and p-values will be presented:

- SP-102/none vs. PBO/none

- SP-102/SP-102 vs. PBO/none
- SP-102/none vs. PBO/SP-102
- SP-102/SP-102 vs. PBO/SP-102

A summary of the assessments at Weeks 16, 20, and 24 will be presented.

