#### **7.12.6.2 The time (days) to repeat injection of SP-102**

The time to repeat injection of SP-102 will be analyzed using survival analysis methods. Subjects that do not receive a repeat injection will be censored at 20 weeks, and subjects who discontinue the study prior to 20 weeks without receiving a repeat injection will be censored at the time of discontinuation. The Kaplan-Meier estimator will be used to estimate the quartiles of the time to repeat injection in days. A Cox proportional hazards model will be utilized to test the treatment difference in time to repeat injection while adjusting for site, and Pain Catastrophizing Scale. The response variable of the Cox model will be time to repeat injection. The treatment group categories for this analysis will be the SP-102 and placebo groups. The quartiles and their corresponding 95% CIs from the Kaplan-Meier estimation, and the hazard ratio of SP-102 to placebo with its 95% CI and p-value will be presented. A survival plot of time to repeat injection will also be presented. Listings of time to repeat injection will be presented.

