#### **7.12.6.10 Proportion of subjects achieving a response of 30%, 50%, and 75% reductions from Baseline (D1) in mean NPRS average pain score in the affected leg at Week 2 and Week 4.**

Responders are defined and calculated as follows:

30% responder =  $(\text{Change from baseline} / \text{baseline}) \times 100 \leq -30$ .

50% responder =  $(\text{Change from baseline} / \text{baseline}) \times 100 \leq -50$ .

75% responder =  $(\text{Change from baseline} / \text{baseline}) \times 100 \leq -75$ .

Subjects that discontinue or have missing scores at Week 2 and Week 4 will be considered non-responders.

The proportion of subjects achieving a response will be analyzed for each cut off percentage (30%, 50%, and 75%) by week. This will be analyzed using a Chi-Square test where the p-value of the treatment difference will be presented. For each cutoff response percentage, a logistic regression models with treatment (two groups: SP102 or placebo), site, Pain Catastrophizing Scale group ( $<30$  or  $\geq 30$ ), and baseline averaged daily leg pain score as factors will also be used to compare the treatment groups at each week. The odds ratio of SP-102 vs placebo, its corresponding 95% CI and p-value will be presented. The number and percentage of responders will be presented for each visit.

A continuous responder analysis will also be performed. The proportion of subjects achieving a reduction in pain will be plotted against the continuous cutoff ranging from 0% to 100% reduction in pain intensity from Baseline (D1) as measured by the NPRS average daily leg pain scores in the

affected leg. This analysis will be performed using data observed at Week 4 and then over the first 4 weeks (using average of the 4 weekly mean NPRS average daily leg pain scores in the affected leg to calculate the percent reduction). All subjects who withdraw early from the study within 4 weeks will be considered non-responders. Treatment groups (SP-102 and placebo) will be compared using a log rank test.

**7.12.6.11 The mean change from Baseline (D1) to Week 2, Week 4, Week 8, and Week 12 in mean NPRS average pain score in the lower back.**

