**7.12.6.12 CGIC at Week 2, Week 4, Week 8, and Week 12.**

The CGIC is an 8-point scale (0 to 7, where 0 is not assessed, 1 is very much improved, and 7 is very much worse) that allows clinicians to rate the subject's global impression of change. CGIC will be collected after randomization at Weeks 2, 4, 8, 12, 16, 20, and 24. For analysis, a subject will be classified as either CGIC responder, that is, a CGIC response of 1: very much improved or 2: much improved or a CGIC non-responder, that is, all other CGIC responses (recorded as 3-7 in the scale). Subjects who do not complete the measure at the timepoint of interest will also be considered non-responders. The number and percentage of subjects reporting each of the seven

CGIC response levels will also be summarized by visit and treatment. Analyses will utilize separate Chi-Square tests for Week 2 and Week 4 where the p-value of the treatment difference will be presented. Separate logistic regression models with treatment, site, and Pain Catastrophizing Scale group ( $<30$  or  $\geq 30$ ) as factors will also be used to compare the treatment groups for Week 2 and Week 4 using the 2 treatment groups. The odds ratio of SP-102 vs placebo at Weeks 2 and 4, and its corresponding 95% CI and p-value will be presented. Listings of CGIC will also be provided.

Separate Chi-Square tests and similar logistic regression analyses will be applied at Weeks 2, 4, 8, and 12 using the treatment group with four arms: SP-102/SP-102, PBO/SP-102, SP-102/none, PBO/none. The following odds ratios at Weeks 2, 4, 8, and 12 and the corresponding 95% CIs and p-values will be presented:

- SP-102/none vs. PBO/none
- SP-102/SP-102 vs. PBO/none
- SP-102/none vs. PBO/SP-102
- SP-102/SP-102 vs. PBO/SP-102

A summary of the assessments at Weeks 16, 20, and 24 will be presented.

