#### **7.12.6.13 Cumulative use of rescue medication (mg of acetaminophen)**

In this study, acetaminophen is the permitted and study-provided rescue medication. For subjects that withdraw early, their missing weekly values after withdrawal will be imputed using the average weekly score for the respective treatment group. If the subject has partial records of rescue medication on the week of subject's withdrawal, the rescue medication use on that week will be imputed as follows:

[ partial record of rescue medication on the withdrawal week \* (7/number of days in the withdrawal week with partial record) ].

Cumulative use of rescue medication at Week 4 will be obtained as the rescue medication use during the first four weeks relative to the index injection, that is, up to the subject's Day 29 in the study. It will be analyzed using an analysis of variance (ANOVA) model with cumulative use from baseline to Week 4 as the response variable with fixed effects for treatment (two groups: SP102 or placebo), site, and Pain Catastrophizing Scale group ( $<30$  or  $\geq 30$ ). The same ANOVA model will

be applied on only subjects that complete 4 Weeks and output will be presented using the two treatment groups.

Cumulative use of rescue medication at Week 12 will be obtained as the rescue medication use during the first 12 weeks relative to the index injection, that is, up to subject's Day 85 in the study. It will also be analyzed using an ANOVA model with cumulative use from baseline to Week 12 as the response variable with fixed effects using the four treatment (SP-102/SP-102, PBO/SP-102, SP-102/none, PBO/none) variable, site, and Pain Catastrophizing Scale group (<30 or ≥30). The same ANOVA model will be applied on only subjects that complete 12 Weeks and output will be presented using the four treatment groups.

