#### **7.12.6.14 Time to first rescue medication dose**

The time to first rescue medication dose, in days, will be analyzed like the time to event endpoint in [Section 7.11.6.2](#). Time to first rescue medication dose will be analyzed separately for the first 4 weeks (two groups), and the first 12 weeks (four groups). For both analysis periods, time to first rescue medication dose will be calculated relative to the date of index injection. For the primary analysis period (first 4 weeks), subjects who do not use rescue medications for the first 4 weeks will be censored at Day 29th while subjects who discontinue the study prior to the subject's Day 29th in the study will be censored at the time of discontinuation. Similarly, for the secondary analysis period, subjects who do not use rescue medication for the first 12 weeks will be censored at Day 85th while subjects who discontinue the study prior to the subject's Day 85th in the study will be censored at the time of discontinuation.

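### The PGIC, CGIC, repeat-injection and rescue-use models carry no baseline pain term; adding baseline leg pain, which is already collected, would gain some power at almost no cost

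*SAP*

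**What the plan says.** Five endpoints in SAP 7.12.6 are analysed with treatment, pooled site and the Pain Catastrophizing Scale (PCS) as the only model terms.

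- **PGIC (7.12.6.1).** Two analyses are given. First, "The analysis will utilize separate Chi-Square tests for Week 2 and Week 4", with a p-value. Then: "Separate logistic regression models with treatment, site, and Pain Catastrophizing Scale group as factors will also be used to compare the treatment groups".
- **CGIC (7.12.6.12).** The same pair of analyses, the second being "Separate logistic regression models with treatment, site, and Pain Catastrophizing Scale group".
- **Time to repeat injection (7.12.6.2).** A Cox model is used to "test the treatment difference in time to repeat injection while adjusting for site, and Pain Catastrophizing Scale".
- **Time to first rescue dose (7.12.6.14).** This "will be analyzed like the time to event endpoint in" Section 7.11.6.2. The section meant is evidently 7.12.6.2, so the covariates are the same.
- **Cumulative rescue use (7.12.6.13).** An ANOVA with cumulative use to Week 4 "as the response variable with fixed effects for treatment (two groups: SP102 or placebo), site, and Pain Catastrophizing Scale group". The Week 12 model has the same terms with four treatment groups.

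Two other analyses in the same section do adjust for baseline leg pain. The 12-week repeated-measures model for average leg pain (7.12.6.4) lists the baseline averaged daily leg pain score. The logistic models for 30%, 50% and 75% responders (7.12.6.10) list site, PCS group "and baseline averaged daily leg pain score as factors will also be used to compare the treatment groups at each week".

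Protocol 3.1 has leg pain recorded twice daily from Screening to Day 1, with the last 7 days used for eligibility. SAP 11 records that PGIC was moved from 13th to third in the testing order.

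**The concern.** PGIC and CGIC rate change and have no baseline of their own. Time to repeat injection and rescue use are not given one either. These five analyses therefore contain no measure of how much pain the subject started with.

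For repeat injection and rescue use, a link to baseline pain is plausible from the documents. Qualifying for a repeat injection depends partly on the leg NPRS score, and rescue is for inadequately controlled radicular pain. For PGIC and CGIC a link is possible but less obvious, because both ask about change.

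If baseline pain is prognostic, leaving it out keeps avoidable residual variance in the ANOVA and costs some power in the logistic and Cox models. The score is recorded before randomisation and already used elsewhere in the SAP, so the loss can be avoided without new data.

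**Working it through.** **Inputs from the documents.** About 400 subjects randomised 1:1, with a goal of 332 completing Week 4 (Protocol synopsis), so 332/2 = 166 per arm if split equally. Two-sided 5% level (SAP 7.12). The sample size justification is blacked out, so there is no planned power figure to reproduce. Every effect size and prognostic strength below is my assumption.

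**1. Cumulative rescue use: ANOVA against ANCOVA.** Set the effect so that power without the covariate is 80% at 166 per arm: standardised difference = (1.960 + 0.842) × √(2/166) = 0.3075. A baseline–outcome correlation r multiplies the residual SD by √(1 − r²), so power becomes Φ(2.802/√(1 − r²) − 1.960). For r = 0.3: 2.802/0.954 = 2.937, and Φ(0.977) = 83.6%.

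| r | Variance removed | Power with covariate | Subjects per arm for the original 80% |
|---|---|---|---|
| 0.1 | 1% | 80.4% | 165 |
| 0.2 | 4% | 81.6% | 160 |
| 0.3 | 9% | 83.6% | 152 |
| 0.4 | 16% | 86.4% | 140 |
| 0.5 | 25% | 89.9% | 125 |

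**2. PGIC or CGIC responder: logistic model.** Simulation with 166 per arm, responder rates of 25% and 39%, a standard-normal baseline score and 4,000 runs per scenario. Site and PCS terms were left out for simplicity. The chi-square formula gives 78.3% power for these rates, in line with the unadjusted column.

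| Odds ratio per SD of baseline pain | Power without | Power with | Treatment odds ratio without / with |
|---|---|---|---|
| 1.25 | 77.7% | 78.0% | 1.93 / 1.94 |
| 1.5 | 78.8% | 79.7% | 1.92 / 1.97 |
| 2.0 | 77.8% | 82.2% | 1.93 / 2.06 |
| 3.0 | 79.0% | 85.9% | 1.93 / 2.24 |

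Monte Carlo error on each power figure is about √(0.79 × 0.21/4000) = 0.6 points, so the first row shows no measurable gain. Type I error was 4.5% to 5.4% with or without the covariate.

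**3. Time to event: Cox model.** Simulation with 200 per arm, true hazard ratio 0.68 and 1,500 runs.

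| Log hazard ratio per SD of baseline pain | Power without | Power with | Unadjusted hazard ratio |
|---|---|---|---|
| 0.2 | 72% | 73% | 0.68 |
| 0.4 | 69% | 73% | 0.69 |
| 0.6 | 65% | 74% | 0.71 |

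These depend on the event rate, which the documents do not give. By Schoenfeld's formula, 73% power at a hazard ratio of 0.68 needs 4 × [(1.960 + 0.613)/ln 0.68]² ≈ 178 events, or 178/400 = 44.5% of subjects. A repeat run at that event rate gave gains within one point of those in the table.

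**The case against.** **The tests are valid without the covariate.** This stands. A reader might infer that the omission biases the treatment comparison. It does not for the two randomised arms: type I error is unaffected. Most of the apparent drift of the odds or hazard ratio toward 1 is non-collapsibility. The models with and without baseline pain estimate a conditional and a less conditional effect, which are different targets; neither is a faulty version of the other. (The four-group comparisons are formed after randomisation. They raise a separate question that this covariate does not settle.)

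**The SAP is arguably consistent.** Its visible pattern is to adjust each outcome for its own baseline: ODI, PainDETECT and BPI-SF each use their own score, and the two analyses that use leg pain are themselves leg-pain outcomes. This largely stands, so the point is a missed improvement and not a broken rule.

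**PGIC's place in the sequence may be untouched.** A reader might infer that the missing covariate could stop the fixed sequence at its third step. The visible text does not support this. SAP 7.12.6.1 gives the unadjusted chi-square p-value first and introduces the logistic models as additional, and the ordered list in 7.12.6.19 is blacked out. If the chi-square is the gate, adding a covariate to the logistic model changes nothing there.

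**Prognostic strength is not documented.** Also true. Eligibility was screened on pre-randomisation NPRS scores, which could narrow the range of baseline pain and weaken it as a predictor. The repeat-injection criteria apply 4 to 20 weeks after the index injection and are blacked out, so the baseline score itself is not shown to determine who qualifies. The protocol's secondary-analysis text is blacked out too, so whether it planned this covariate cannot be checked.

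What remains is that the covariate is absent from all five endpoints, is available, and costs almost nothing to include.

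**Conclusion.** The point holds as an improvement in efficiency, not as an error. The gain is below about 2 points of power if baseline pain is weakly prognostic (correlation up to 0.2, odds ratio per SD up to 1.5, or log hazard ratio per SD of 0.2). It is about 4 or more points if baseline pain is moderately to strongly prognostic (correlation of 0.3 or above, odds ratio per SD of 2 or above, or log hazard ratio per SD of 0.4 or above); the largest gain in the scenarios tried is about 10 points. All of this rests on assumed effect sizes, event rates and prognostic strength.

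The argument is best for repeat injection and rescue use. For PGIC and CGIC it is weaker, and any effect on the testing sequence is conditional on the adjusted logistic model being the gatekeeping test, which the visible text does not say.

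**What to change.** Before unblinding, amend the SAP as follows.

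- Add baseline averaged daily leg pain as a continuous covariate to the models in 7.12.6.1, 7.12.6.2, 7.12.6.12, 7.12.6.13 and 7.12.6.14, as in 7.12.6.10.
- State that the reported odds and hazard ratios are conditional on baseline leg pain as well as on site and PCS.
- In 7.12.6.1 and 7.12.6.19, name the single PGIC test that gates the sequence. If the covariate is meant to help at that step, name the adjusted logistic model in place of the chi-square. If the chi-square stays as the gate, make no claim that the covariate affects the sequence.
- Correct the cross-reference in 7.12.6.14.

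The cost is a wording change and one degree of freedom per model, with no new data. The change must be fixed in advance because it alters which effect the odds and hazard ratios describe.
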